#### **11.1.3 Standard Pure Tone Audiometry**

Standard Pure Tone Audiometry will be measured to determine a subject's threshold for hearing at various frequencies and will be performed at the Screening visit and Day 15, 60, 90, 150, and 210. This will be performed on a calibrated audiometer by a licensed audiologist. The following frequencies will be obtained: Air: 250 Hz, 500 Hz, 1 kHz, 2 kHz, 3 kHz, 4 kHz, 6 kHz, and 8 kHz; Bone: 500 Hz, 1 kHz, 2 kHz, 3kHz, and 4 kHz.

### **11.2 Exploratory Efficacy Measurements Assessed**

#### **11.2.1 Extended High Frequency Audiometry**

Extended high frequency audiometry will be performed to determine a subject's threshold for hearing at frequencies beyond those in standard pure tone audiometry and will be performed

at the screening visit and Day 15, 60, 90, 150, and 210. This will be performed on a calibrated audiometer by a licensed audiologist. The following frequencies will be obtained: Air – 9 kHz, 10 kHz, 11.2 kHz, 12.4 kHz, 14 kHz, and 16 kHz.

### **11.2.2 Tinnitus Functional Index (TFI)**

The Tinnitus Functional Index has eight subscales that address the intrusiveness of tinnitus, the sense of control the patient has, cognitive interference, sleep disturbance, auditory issues, relaxation issues, quality of life, and emotional distress. The subject will report (either directly onto the questionnaire in person, via web, or over the phone) answers to each of the 25 questions using a scale of 0-10. The TFI will be given to the subject to complete at the Baseline, Day 60, Day 120, and Day 210 visits.

### **11.2.3 Hearing Handicap Inventory for Adults (HHIA)**

The Hearing Handicap Inventory for Adults (HHIA), is a 25-item self-assessment scale composed of two subscales (emotional and social/situational). The subject will report (either directly onto the questionnaire in person, via web, or over the phone) one of the following answers for each item on the scale: Yes, Sometimes, No. The HHIA will be given to the subject to complete at the Baseline, Day 60, Day 120, and Day 210 visits.

### **11.2.4 Hearing Screening Inventory (HSI)**

The Hearing Screening Inventory is a 12 item self report inventory to assess hearing impairment. The subject will self report one of the following answers, for each question from 1 to 8: Never, Seldom, Occasionally, Frequently, Always, and for each question from 9 to 12: Good, Average, Slightly below average, Poor, Very Poor. The HSI is designed to assess subjective change during the study and will be given to the subject to complete at the Baseline and Day 210 visits.

## **12 SAFETY ASSESSMENTS**

The planned schedule of assessments is in Section **Error! Reference source not found..**

### **12.1 Safety Measurements Assessed**

#### **12.1.1 Concomitant Medication**

Subjects will be asked about concomitant medications at time points outlined in the Table of Assessments. All concomitant medication information will be recorded in the eCRF.

#### **12.1.2 Clinical Laboratory Evaluation**

Blood samples will be collected for safety laboratory assessments for clinical chemistry and a complete blood count.

Urine drug screen (cocaine, narcotics, benzodiazepines, tetrahydrocannabinol, barbiturates, and amphetamines) will be performed at Screening only.

Screening for pregnancy will be performed (urine  $\beta$ -HCG) as outlined in Table 1.

### **12.1.3 Vital Signs**

Vital signs (temperature, blood pressure and heart rate) will be recorded at time points outlined in Table 1 and will be performed in a standardized manner, i.e., after the subject has rested in the sitting position for 5 minutes.

### **12.1.4 Physical Exam (PE)**

A complete physical examination will be performed by a licensed provider at Screening.

Complete physical examinations include: general appearance, head, ears, eyes, nose, throat, dentition, thyroid, chest (heart, lungs), abdomen, skin, neurological, extremities, back, neck, musculoskeletal, and lymph nodes and any pertinent system based on any prior findings. Physical examinations may be performed at various unscheduled time points, if deemed necessary by the Investigator.

### **12.1.5 Columbia Suicide and Severity Rating Scale (C-SSRS)**

This scale is used to determine if any suicide ideation or intention is present. The questionnaire is read aloud to the subject and responses are recorded by the trained staff member. If any ideation or intention is present, the Investigator will interview the subject and have them follow up with their primary healthcare provider. The C-SSRS will be completed at the Baseline, Day 60, Day 120, and Day 210 visits.

### **12.1.6 Body Mass Index (BMI)**

BMI will be calculated by dividing the subject's body weight in kilograms by the subject's height in meters squared ( $BMI = \text{kg}/\text{m}^2$ ). Body height (centimeter) and body weight (kilograms) will be measured at the time points delineated in the Schedule of Assessments.

### **12.1.7 Otoscopy**

Microscopic otoscopy will be included to specifically record any abnormalities of the external ear canal, tympanic membrane and middle ear and will be performed at Screening, prior to injection on Day 1, 8, 15, and 21 and at the Day 60, 90, 150, and 210 visits.

### **12.1.8 Tympanometry**

Tympanometry (an objective test of tympanic membrane mobility) tests the integrity of the tympanic membrane by varying air pressure in the ear canal. Middle ear compliance, peak pressure, and tympanogram type will be recorded. Tympanometry will be performed at the Screening, Day 15, and at the Day 60, 90, 150, and 210 Visits. The assessment will be performed by a licensed audiologist on a calibrated tympanometer. A print-out containing the tympanometry from the machine will be collected and stored in the source document.

## 13 ADVERSE EVENTS

### Adverse Event Definition

An AE is defined as any untoward medical occurrence in a clinical study subject administered a medicinal product which does not necessarily have a causal relationship with this treatment. An AE can therefore be any unfavorable and unintended sign (including an abnormal laboratory finding), symptom, or disease temporally associated with the use of a medicinal (investigational) product, whether or not it is related to the medicinal (investigational) product. This includes an exacerbation of pre-existing conditions or events, intercurrent illnesses, drug interaction or the significant worsening of the indication under investigation that is not recorded elsewhere in the eCRF under specific efficacy assessments. Anticipated fluctuations of pre-existing conditions, including the disease under study that do not represent a clinically significant exacerbation or worsening need not be considered AEs.

It is the responsibility of the investigator to document all AEs that occur during the study. AEs will be elicited by asking the subject a nonleading question, for example, "Have you experienced any new or changed symptoms since we last asked/since your last visit?". AEs will be recorded from the time of the first treatment through the end of the follow up period. AEs should be reported on the appropriate page of the eCRF.

### Unexpected Adverse Event or Unexpected Suspected Adverse Reaction Definition

An adverse event or suspected adverse reaction is considered "unexpected" if it is not listed in the investigator brochure or is not listed at the specificity or severity that has been observed; or, if an investigator brochure is not required or available, is not consistent with the risk information described in the general investigational plan or elsewhere in the current application, as amended.

"Unexpected," as used in this definition, also refers to adverse events or suspected adverse reactions that are mentioned in the investigator brochure as occurring with a class of drugs or as anticipated from the pharmacological properties of the drug, but are not specifically mentioned as occurring with the particular drug under investigation.

### Assessment of Severity

Each AE will be assigned a category by the investigator as follows:

- Mild: An AE that is easily tolerated by the subject, causes minimal discomfort and does not interfere with everyday activities.
- Moderate: An AE that is sufficiently discomforting to interfere with normal everyday activities; intervention may be needed.
- Severe: An AE that prevents normal everyday activities; treatment or other intervention usually needed.

If there is a change in severity of an AE, it must be recorded as a separate event.

### Assessment of Causality

Every effort will be made by the investigator to assess the relationship of the AE, if any, to the study drug. Causality should be assessed using the categories presented in the following table:

- Not Related: Clinical event with an incompatible time relationship to study drug administration, and that could be explained by underlying disease or other drugs or chemicals or is incontrovertibly not related to the study drug.
- Unlikely: Clinical event whose time relationship to study drug administration makes a causal connection improbable, but that could plausibly be explained by underlying disease or other drugs or chemicals.
- Possible: Clinical event with a reasonable time relationship to study drug administration, but that could also be explained by concurrent disease or other drugs or chemicals.
- Related: Clinical event with a reasonable time relationship to study drug administration and is unlikely to be attributed to concurrent disease or other drugs or chemicals.

### **Adverse Events of Special Interest (Audiometric and Otoloscopic)**

If any of the following criteria are met, the event will be recorded as an adverse event of special interest (AESI) per ASHA guidelines (ASHA 1994):

- Asymmetric loss of hearing greater than 20 dB at any one frequency in the treated ear compared to the Screening Visit.
- Asymmetric loss of hearing greater than 10 dB at two adjacent frequencies in the treated ear compared to the Screening Visit.
- Asymmetric loss of response at three consecutive test frequencies where responses were previously obtained in the treated ear compared to the Screening Visit.

For word recognition testing, a follow up visit score in the treated ear that falls below the lower limit of the 95% confidence interval of the baseline word recognition score will be considered an AESI (Thorton and Raffin 1978).

Additionally, if the subject experiences a perforation greater than 25% of the tympanic membrane in the treated ear this will be recorded as an AESI.

If any subjects in the study experience the same AESI, the Medical Monitor will discuss these with the Principal Investigators and each subject's condition will be discussed. The Medical Monitor, in consultation with the sponsor, will determine whether to proceed with any future doses if the subjects have not completed all 4 doses.

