### **8.4.2 Inclusion Criteria**

To be eligible for study entry subjects must satisfy all of the following criteria:

1. Subject has read and voluntarily signed the Informed Consent Form (ICF) after all questions have been answered and prior to any study-mandated procedure.
2. Adult aged 18-65 years inclusive.
3. Established diagnosis of stable sensorineural hearing loss by standard audiometric measures for  $\geq 6$  months prior to the Screening visit (no changes in air conduction greater than 10 dB at a single frequency or greater than 5dB at two contiguous frequencies from the prior audiogram to the Screening audiogram in the study ear).
4. Documented medical history consistent with hearing loss being caused by noise exposure or sudden sensorineural hearing loss (documented audiogram at least 6 months prior to screening required).
5. A pure tone average of 26-70 dB at 500Hz, 1000Hz, 2000Hz, and 4000Hz in the ear to be injected.
6. Subjects with a 15% - 85% correct score on Word Recognition test (8 – 42 words correct out of 50) at Screening in the study ear.
7. Ability to communicate well with the Investigator and is willing to comply with and complete all the study procedures.
8. Female subjects must be of non-childbearing potential or will need to utilize two methods of highly effective contraception during the study participation (e.g. hormonal contraception or an intrauterine device and condoms) or remain abstinent. Male subjects

should use condoms with spermicide during the course of the study or remain abstinent. Subjects should not donate sperm or ova during the study period.

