### 7.3.9. Clinical Improvement in WR, using Thornton-Raffin Confidence Intervals ( $CI_{TR}$ )

- *Computation of the Endpoint*

Clinical improvement in WR at post-baseline visits for treated ears will be defined by comparing Thornton-Raffin (1978) 95% confidence intervals ( $CI_{TR}$ ) (Section 14.1) at the baseline visit versus the percentage of recognized words at the post-baseline visits. It will be defined as 'Improved' if the subject's post-baseline score is higher than the upper limit of the subject's baseline 95%  $CI_{TR}$ , as 'No change' if the post-baseline score falls within or on the bounds of the baseline 95%  $CI_{TR}$ , and 'Reduction' if the post-baseline score is lower than the baseline lower limit of the 95%  $CI_{TR}$ .

The Thornton-Raffin 95%  $CI_{TR}$  reported in Section 14.1 will be used directly and not computed.

- *Analysis of the Endpoint*

The incidence of clinical improvement in WR (Improvement, No Change, Reduction) based on  $CI_{TR}$  at each post-baseline visit for treated ears will be summarized using frequencies and percentages by visit and treatment group for subjects in the FAS.

Scatter plots will be used to summarize clinical improvement in the percentage of recognized words (Section 7.3.2) in treated ears. The percentage of recognized words at baseline will be plotted on the x-axis and the percentage of recognized words post-baseline will be plotted in the y-axis, with a separate plot for each post-baseline visit. The baseline Thornton-Raffin 95% confidence intervals in Section 14.1 will be overlaid in the plot.

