### 7.5.2. AC and BC Improvement $\geq$ 10 dB from baseline for two contiguous frequencies

- *Computation of the Endpoint*

AC Improvement  $\geq$ 10 dB from baseline for two contiguous frequencies at each post-baseline visit for treated ears will be computed as 1 if the post-baseline threshold – baseline threshold is  $\geq$ 10 dB for two contiguous frequencies and as 0, otherwise. The endpoint will utilize imputed values per Section 7.5. The BC Improvement  $\geq$ 10 dB will be derived using the same approach.

- *Analysis of the Endpoint*

The incidence of AC improvement  $\geq 10$  dB from baseline for two contiguous frequencies at each post-baseline visit for treated ears will be summarized using frequencies and percentages by visit and treatment group for subjects in the FAS. The summary will be repeated for BC improvement.

In treated ears only for subjects in the FAS, treatment group comparisons for incidence of AC improvement  $\geq 10$  dB from baseline for two contiguous frequencies may be analyzed using a generalized estimating equation based on the binomial distribution with logit link. The fixed covariates may include treatment group, WR score at baseline (<50% versus  $\geq 50\%$ ), etiology of hearing loss (SSNHL versus NIHL), visit, and interaction between visit and treatment group. Covariates for WR score at baseline and etiology of hearing loss may be dropped if the model fails to converge. A random effect for within-subject, repeated measures variability may be included. The treatment group differences analyzed will be between each FX-322 group (including the pooled FX-322 group) versus placebo, and comparisons between the individual FX-322 groups (excluding the pooled FX-322 group). Odds ratios, 95% CIs, and p-values may be reported and comparisons will be made by visit and overall. The analysis will be repeated for BC improvement.

- *Sensitivity Analyses of the Endpoint*

The analyses will be repeated for subjects in the PPAS.

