### 7.5.3. AC and BC Improvement $\geq 15$ dB from baseline for any frequency

- *Computation of the Endpoint*

AC Improvement  $\geq 15$  dB from baseline for any frequency at each post-baseline visit for treated ears will be computed as 1 if the post-baseline threshold – baseline threshold is  $\geq 15$  dB for any frequency and as 0, otherwise. The endpoint will utilize imputed values per Section 7.5. The BC Improvement  $\geq 15$  dB will be derived using the same approach.

- *Analysis of the Endpoint*

The incidence of AC improvement  $\geq 15$  dB from baseline for any frequency at each post-baseline visit for treated ears will be summarized using the approach described in Section 7.5.2 for subjects in the FAS. The summary will be repeated for BC improvement.

Treatment group comparisons for AC improvement and BC improvement may be performed using the approach described in Section 7.5.2 for subjects in the FAS.

- *Sensitivity Analyses of the Endpoint*

The analyses will be repeated for subjects in the PPAS.

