#### 7.5.4. AC and BC Composite Improvement

- *Computation of the Endpoint*

The AC Composite Improvement endpoint is defined as the occurrence of either or both of the following conditions for a given subject's ear for a given visit: 1) AC Improvement  $\geq 10$  dB from baseline for two contiguous frequencies as described in Section 7.5.2 or 2) AC improvement  $\geq 15$  dB from baseline for any frequency as defined in Section 7.5.3. BC Composite Improvement is defined using the same approach.

- *Analysis of the Endpoint*

The incidence of AC Composite Improvement at each post-baseline visit for treated ears will be summarized using the approach described in Section 7.5.2 for subjects in the FAS. The summary will be repeated for BC Composite Improvement.

Treatment group comparisons for AC Composite Improvement and BC Composite Improvement may be performed using the approach described in Section 7.5.2 for subjects in the FAS.

- *Sensitivity Analyses of the Endpoint*

The analyses will be repeated for subjects in the PPAS.

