##### 8.4.1. Adverse Events of Special Interest (AESI)

Protocol Section 13 defines adverse events of special interest.

AESIs will be summarized by treatment group and overall for all subjects in the SfAS. The summary will display the total number of AESIs as well as the count and percentage of subjects experiencing any AESI. The total number of AESIs and the count and percentage of subjects experiencing at least 1 AESI in each system organ class and preferred term will also be shown. All percentages will use the number of subjects in the SfAS by treatment group as the denominator. Therefore, if a subject has more than 1 AE within a system organ class, the subject will be counted only once in that system organ class. If a subject has more than 1 AE that codes to the same preferred term, the subject will be counted only once for that preferred term. The tabular summary will be sorted by descending frequency of system organ class and preferred term for overall incidence.

AESIs will be presented in a data listing for subjects in the SfAS.

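### No per-ear count of audiometric worsening is planned at the dB limits used to count improvement, and AESIs are tabulated as filed rather than derived from the audiograms

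*Protocol*

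**What the plan says.** **Gains.** In SAP 7.5.2 the improvement flag is "computed as 1 if the post-baseline threshold – baseline threshold is" at least 10 dB at two contiguous frequencies. SAP 7.5.3 uses at least 15 dB at any one frequency. SAP 7.5.4 joins them: "The AC Composite Improvement endpoint is defined as the occurrence of either or both of the following conditions". This applies to air and bone conduction, and 7.6.2 to 7.6.4 repeat it for extended high frequencies. Frequencies and percentages of treated ears are given by visit and arm, with optional GEE comparisons.

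**Losses.** Protocol Section 13 makes three audiometric findings adverse events of special interest (AESIs): "Asymmetric loss of hearing greater than 20 dB at any one frequency in the treated ear compared to the Screening Visit"; more than 10 dB at two adjacent frequencies; and loss of response at three consecutive frequencies. All three must be asymmetric, a term that neither document defines. A word recognition (WR) score below the lower baseline limit is also an AESI. SAP 8.4.1 refers to the protocol for the definition and says "AESIs will be summarized by treatment group and overall for all subjects in the SfAS", by system organ class and preferred term.

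**General adverse event definition.** Protocol Section 13 includes significant "worsening of the indication under investigation that is not recorded elsewhere in the eCRF under specific efficacy assessments".

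**Two points of comparison.** The WR endpoint in SAP 7.3.9 has a downward class: "Reduction' if the post-baseline score is lower than the baseline lower limit". Inclusion criterion 3 defines stable hearing as "no changes in air conduction greater than 10 dB at a single frequency or greater than 5dB at two contiguous frequencies".

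**The concern.** Hearing loss is a listed risk (Protocol 6.2) and local safety is a primary objective (Protocol 7.1). Yet audiometry is not among the protocol's safety endpoints (7.2) or the safety analyses in SAP 8.1, so counts of ears by size of threshold change can come only from the efficacy section or from filed AESIs. The efficacy section counts one direction. The AESI route has wider limits, an undefined asymmetry condition, and depends on the site recording the event.

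What is at stake is the case of mixed effects. If some treated ears gain and others lose, means and mixed models net the two, while the responder tables show the gains. The reader could not set the number of ears that lost 10 or 15 dB beside the number that gained it.

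**Working it through.** The plan states no figure to reproduce, and the sample size has no formal basis (Protocol 14.1.2). The check compares the limits, asks what the other outputs would show, and illustrates the size of the gap.

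**1. Direction.** SAP 7.5 replaces a post-Screening no-response by the equipment maximum plus 5 dB, so a higher threshold is worse hearing. Post-baseline minus baseline of at least 10 or 15 dB is therefore, read literally, a loss labelled as improvement. The same wording is in 7.5.3, 7.6.2 and 7.6.3, and feeds 7.5.4, 7.6.4 and 7.5.9. The endpoint titles show that a fall is meant. On either reading only one direction is counted.

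**2. Limits side by side.** The 5 dB step is an assumption; the documents do not state it.

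| | One frequency | Two contiguous or adjacent |
|---|---|---|
| Unstable at entry (criterion 3) | >10, i.e. ≥15 dB | >5, i.e. ≥10 dB |
| Improvement (SAP) | ≥15 dB | ≥10 dB |
| AESI loss (Section 13) | >20, i.e. ≥25 dB | >10, i.e. ≥15 dB |

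The entry rule and the improvement rule coincide on this grid. The uncounted band is a loss of 15 or 20 dB at one frequency, or 10 dB at two contiguous frequencies.

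**3. Would the other tables show such a loss?**
- SAP 7.5.1 summarises and models thresholds at each frequency. It gives group values, not a number of ears.
- The PTA in 7.5.5 averages 0.5, 1, 2 and 4 kHz. A 10 dB loss at two contiguous frequencies moves it by 10 × k/4, where k is the number of affected PTA frequencies: 0 dB (6 and 8 kHz), 2.5 dB or 5 dB. A loss of 15 or 20 dB at one PTA frequency moves it by 15/4 = 3.75 or 20/4 = 5 dB; at 0.25, 3, 6 or 8 kHz it moves it by 0. With 15 dB categories and roughly uniform baselines (assumed), the chance of changing category is shift/15, so 0 to 5/15 = 33%.
- The air-bone shift in 7.5.8 uses air minus bone. A loss that raises both equally leaves it unchanged.
- For extended high frequencies, 7.6.6 to 7.6.8 count only shifts from no signal to any signal.

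**4. Simulation of ears with no true change.** Assumed: 400,000 ears per setting, 8 air frequencies, normal retest differences rounded to 5 dB, between-frequency correlation 0 or 0.3. AESI means the one- and two-frequency dB rules only, without the asymmetry condition or the loss-of-response rule.

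| SD of difference (dB) | Improved | Mirror-image loss | AESI dB rules |
|---|---|---|---|
| 4 | 1.3–2.2% | 1.3–2.2% | 0.00–0.01% |
| 5 | 7.1–8.1% | 7.2–8.2% | 0.03–0.17% |
| 6 | 17.0–18.2% | 16.9–18.3% | 0.30–0.90% |
| 7 | 26.5–31.6% | 26.7–31.6% | 1.4–2.7% |
| 8 | 35.4–44.3% | 35.6–44.1% | 4.1–5.7% |

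The AESI dB rules miss 84% to nearly 100% of the mirror-image losses.

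Hand check at SD 6, correlation 0: a rounded change of at least 15 dB in one direction has probability Φ(−12.5/6) = 0.0186. The one-frequency rule alone gives 1 − (1 − 0.0186)^8 = 14.0%; the pair rule supplies the rest of the 18.2%. For the AESI rules, 8 × Φ(−22.5/6) + 7 × 0.0186² = 0.0007 + 0.0024 = 0.3%, as simulated.

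For an arm of 24 at SD 6, that is 24 × 0.170 to 24 × 0.182, or 4.1 to 4.4 ears improved by noise, an equal number worsened, and 24 × 0.003 to 24 × 0.009, or 0.07 to 0.22, meeting the AESI dB rules.

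**5. When randomisation does not cancel this.** If treatment leaves the mean change at zero but widens the spread, say SD 5 on placebo and SD 7 on drug, the table implies about 7 to 8% against 27 to 32% improved. The mirror-image count would show directly that drug ears lose as often as they gain.

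**The case against.** Much of the case on the other side stands.

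- A reader might infer that losses appear only as filed AESIs, or are never tabulated. The documents do not support that. SAP 7.5.1 shows thresholds by frequency, visit and arm for treated and untreated ears; the shift tables in 7.5.5 and 7.5.8 run both ways, and their own examples are worsenings; SAP 7.1.2 lists all data. Protocol 9.1 also requires any new clinically relevant finding to be reported as an adverse event, and SAP 8.3 tabulates ear events by treated and untreated ear.
- A reader might take the simulated rates as a biased comparison. They are not. The planned comparisons are with concurrent randomised placebo, and equal retest noise raises both arms alike. The rates rest on assumed SDs, and at SD 4 they are only 1 to 2%.
- A reader might infer that the general adverse event definition cancels the AESI rule. It does not say so, and the AESI section is specific and mandatory. What remains is two passages that pull in different directions and need reconciling.
- An exploratory response limit and a safety alert may properly differ, and Section 13 attributes its limits to a cited guideline. There is no single primary endpoint and p-values are descriptive. Table specifications sit in separate documents, so extra output may exist there.

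None of this supplies a planned count of ears that worsened at the response limits. The adverse event route depends on clinical judgement, and the shift tables are insensitive to losses of this size.

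**Conclusion.** The gap is real but narrow. SAP 7.5.2 to 7.5.4 and 7.6.2 to 7.6.4 define a one-way responder, with no matching per-ear count of worsening, and SAP 8.4.1 does not derive AESIs from the recorded audiograms. On an assumed 5 dB grid, the losses without a count are 15 or 20 dB at one frequency and 10 dB at two contiguous frequencies. The trial's own entry rule calls changes of that size unstable.

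This is a reporting weakness in an exploratory trial. It changes no stated figure and does not by itself bias a comparison between arms. Its consequence is that mixed effects, or greater variability on drug, would be visible per ear mainly through the gains. The step size, retest SDs, between-frequency correlation and uniform PTA baselines are assumptions; the simulated rates illustrate the gap and are not estimates for this trial.

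**What to change.** 1. In SAP 7.5.2 to 7.5.4 and 7.6.2 to 7.6.4, first define improvement as a fall in threshold (baseline minus post-baseline). Without this, a flag in the opposite direction would count gains. Then add a worsened flag for a rise in threshold, with identical dB limits, and report improved and worsened ears side by side by visit and arm, for treated and untreated ears.
2. In SAP 8.4.1, derive the Section 13 audiometric and WR criteria from recorded data at every visit and show them beside the filed AESIs. The sponsor needs to give the asymmetry condition an operational definition. The WR criterion is close to the downward class already computed in 7.3.9.
3. Reconcile the clause on worsening in the general adverse event definition with the AESI section of Protocol Section 13.

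The AESI limits need not change and no new data are needed. The cost is SAP wording, a clarification in the protocol, a few more tables, and a less favourable-looking responder display.
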